Primary aim: To validate and test the reliability of electronic patient-reported outcome (ePRO) for the evaluation of the complex symptoms and their potential triggers in OAB patients in day-to-day life with the use of the Experience Sampling Method.

Objectives:

1. To assess content validity of the developed ePRO.

Hypothesis: We consider content validity of the ePRO adequate since items were carefully selected based on evidence from qualitative studies. Furthermore, item relevance was judged by a multidisciplinary panel of experts in the fields of urology, gastro-enterology, psychiatry and gynaecology as well as by OAB patients.

2. To assess concurrent validity of the developed ePRO.

Hypothesis: We hypothesize to find good correlations between ESM scores (*i.e.* the newly developed ePRO) and 'concurrent' instruments (*i.e.* conventional retrospective questionnaires), since we purport to measure the same constructs with both methods. However, ESM measures real-time symptoms whereas our conventional questionnaires measure retrospectively. Therefore, we do not expect to find perfect correlation coefficients, *i.e.* >0.8. Correlation coefficients between 0.4 and 0.8 are considered appropriate. Correlation coefficients lower than 0.4 reflect very weak or no correlation between the methods, which probably means that we are measuring some other construct with our new ePRO than is measured with the conventional method (current 'gold standard'). On the contrary, correlation coefficients higher than 0.8 reflect very strong correlations, meaning that we are more or less measuring exactly the same construct. In this case, there is no rational for replacing the conventional methods by the new (more intensive) method. For each correlation coefficient its significance will be checked as well.

3. To assess internal consistency of the developed ePRO.

Hypothesis: We hypothesize that internal consistency of the ePRO will be moderate to good, since items were based on theoretical constructs as described in literature. Therefore, we expect to find correlation coefficients (Cronbach's α) of >0.6.

4. To assess test-retest reliability of the developed ePRO.

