4.2 Study procedures

Participants will accomplish the Experience Sampling Method for seven consecutive days during their regular daily life. Previous ESM validation studies validated for the use of the ESM for seven days too.⁴³

During the last three consecutive days of the ESM, patients will also keep a SR-BD following the standard of care. A 7-day voiding diary is a reliable and valid method for documenting the change in symptoms of overactive bladder in men and women with predominantly urge incontinence. However, 3-day voiding diaries are as accurate as the 7-day diary, but patient burden is reduced. Therefore, a 3-day sensation-related bladder diary is used in the standard of care of the department of Urology of MUMC+, Zuyderland Heerlen/Sittard and University Hospital Antwerp.^{46,47} Furthermore, during the first four days of the study, ESM outcomes are not influenced by outcomes reported with the sensation-related bladder diaries. This is in alignment with previous studies.^{4,43}

On the last day of the study period, participants will fill out the several retrospective symptom questionnaires.

To accomplish the ESM, they need to carry their own smartphone or (in case they do not have one) another digital device, which will be lent to them for this period. On the smartphone or digital device an application, specifically developed for this project, will be downloaded. This application will run the PROM as follows.

The concerning device will send out an auditory signal 10 times a day at random moments between 07:00 am and 22:00 pm. During 10 minutes following the signal participants can complete a questionnaire, *i.e.* the developed PROM, on the device (see F1. 'ESM_Vragenlijst_Versie 1.0 (11.08.2017)'). After these 10 minutes the questionnaire will not be available until the next beep and is considered missing data. Therefore, subjects are instructed to complete as many questionnaires as possible each day, as soon as possible following each beep, but to pass over questionnaires when completing is impossible. For example, subjects should not fill out questions when driving a car. The questions will be identical between the different moments during the day.

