6. STATISTICAL ANALYSIS

Part I – Comparison of the ESM to SR-BDs and other retrospective questionnaires

In case of incomplete ESM data, we will not use imputation techniques as these techniques have similar assumptions on the mechanisms of missing data as the statistical model described in the remaining text.

Experience Sampling Methods produce complex multilevel data structures, and analysis techniques need to take the variation between subjects and repeated measures within subjects into account. Associations between urological symptom scores of the SR-BD and corresponding ESM scores will be tested using linear mixed-effects models, with a random intercept to account for clustering of measurements within patients, and an autoregressive (AR1) covariate structure to account for correlations of measurements over time. Currently the SR-BD can be seen as the standard method and will therefore be used as dependent variable in the analysis. For each participant, ESM day-mean scores of individual symptoms will be used as predictor, to test whether average symptom scores of the day reflect the day-mean SR-BD scores.

To quantify the difference of scores between the two methods, ESM data will be subtracted from corresponding day-mean SR-BD scores, resulting in a delta score, which will be statistically tested using the same multilevel analysis, adjusting for repeated measures. In like manner, the differences between the mean SR-BD scores and ESM maximum scores of the day will be tested.

To investigate if certain patient characteristics lead to a different retrospective perception of urgency, possible predictors of a larger delta-score (i.e. the differences in urgency reporting between ESM day-mean scores and the day-mean SR-BD scores) will be tested: i.e. gender, age, presence of comorbid panic disorder and psychological symptoms (HADS).

Part II Validation

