- Internal consistency is a reliability measure to analyse correlations between single items of an instrument/scale that are supposed to measure similar symptoms or domains. The homogeneity of a scale (*e.g.* internal consistency) is analysed by Cronbach's α-statistic. A coefficient of at least 0.6 is generally considered as acceptable, values above 0.8 are considered as good to very good ^{29,64-66}. As subjects are usually not able to respond after every beep (for example because of driving a car), completion of ≥6 of the 10 beep-questionnaires per day will be considered as being compliant. Not completed beep-questionnaires will be considered as missing values in the analyses.^{1,67}
- Test-retest reliability reflects the consistency between repeated measurements of the same outcome in the same test conditions, but at different times. We will ascertain on individual response consistency over the study period. Scores of the first half-week will be correlated with scores of the second half-week. A test-retest reliability coefficient of more than 0.70 will be considered adequate ²⁹.
- Differences between OAB symptom scores assessed by the OAB-q / ICIQ-FLUTS / IPSS and ESM could only be analysed on subject level, by paired sample t-test, due to lack of intra-subject variation in the OAB-q scores (only one measurement per subject). Scoring scales of the retrospective questionnaires and ESM will be harmonized by rescaling the ESM data from a 11-point to a 6-point and 5-point scale. In order to assess whether the rescaling affected the reliability of urological symptom related questions in ESM, a Cronbach's a was calculated for the original and rescaled data. Subject-means (i.e. means over 7 days) of ESM data were calculated and compared to the corresponding OABg / ICIQ-FLUTS /IPSS scores.
- Following the COSMIN guidelines it should be aimed to assess the responsiveness of the ESM tool too. However, since responsiveness is the sensitivity of an instrument to detect difference between two points in time within groups⁶⁸, this psychometric property, it is not meaningful to assess this, since the ESM measures repeatedly over a longer period of time (10 times a day for 7 days). It is expected that there will be a fluctuation of symptoms during the assessment period, however 'big' differences that could be assessed with statistical analysis are not expected to occur. The

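### Section 6.1 plans Cronbach's alpha with no stated unit and no split between within-person and between-person consistency, so it does not test the momentary consistency the ePRO is meant to have

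*Combined protocol and SAP*

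**What the plan says.** Internal consistency is objective 3 of Part II in section 1, where the sponsor writes "we expect to find correlation coefficients (Cronbach's α) of >0.6". In section 6.1 it "is analysed by Cronbach's α-statistic", with the benchmark: "A coefficient of at least 0.6 is generally considered as acceptable, values above 0.8 are considered as good to very good".

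The same bullet adds that "completion of ≥6 of the 10 beep-questionnaires per day will be considered as being compliant" and that "Not completed beep-questionnaires will be considered as missing values in the analyses". It does not name the row of the alpha analysis (beep, day or person), and it gives no within-person or between-person version of alpha. No standard error, confidence interval or test for alpha is planned.

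Elsewhere the nesting is acknowledged. The Part I text of section 6 states that "analysis techniques need to take the variation between subjects and repeated measures within subjects into account", and both Part I and the concurrent-validity and delta-score bullets of section 6.1 use random-intercept models with an AR1 structure.

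**The concern.** Experience-sampling data contain two kinds of item correlation. Between persons, patients with high average urgency may also have high averages on other items. Within persons, the items may or may not rise and fall together from one beep to the next. Ordinary alpha does not distinguish them.

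The Introduction justifies the ePRO by its ability to capture variation over the day, and the end of section 6.1 gives recognition of symptom patterns as the aim. Within-person consistency is therefore the property that matters for the intended use. The Summary makes psychometric properties the main outcome, and alpha is one of the few of these with a numerical criterion. A value above 0.6 could be reported as evidence of reliable momentary measurement when it comes mostly from stable differences between patients.

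**Working it through.** **The plan's own figures.** The limits 0.6 and 0.8 are cited conventions and cannot be recomputed. The 50 evaluable patients of section 3.4 are used in step 4. The matching enrolment of 66 is reproduced by 50/(1 − 0.232) = 65.1, rounded up to 66; the rounded 23% gives 64.9, so 65. It does not enter alpha.

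**Inputs from the documents.** The device "will send out an auditory signal 10 times a day at random moments" for seven days. A patient who meets the compliance rule every day gives 6 × 7 = 42 to 10 × 7 = 70 beeps, so 50 patients give 2,100 to 3,500 beep rows.

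**Assumed inputs (none is in the documents).** Number of items k; share p of item variance lying between persons; between-person item correlation rB; within-person item correlation rW. Items have equal variances and, for the calculations below, no serial correlation within a person.

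**Formulas.** With mean inter-item correlation r, alpha = k·r / (1 + (k − 1)·r), where
- pooled beeps: r = p·rB + (1 − p)·rW
- within persons: r = rW
- person means over m beeps: r = [p·rB + (1 − p)·rW/m] / [p + (1 − p)/m]

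**Step 1. How far the levels can diverge.** k = 4, p = 0.5, rB = 0.6, m = 42:

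| rW | pooled r | pooled alpha | within-person alpha | person-mean alpha |
|---|---|---|---|---|
| 0 | 0.30 | 1.20/1.90 = 0.63 | 0 | 0.85 |
| 0.1 | 0.35 | 1.40/2.05 = 0.68 | 0.40/1.30 = 0.31 | 0.85 |
| 0.2 | 0.40 | 1.60/2.20 = 0.73 | 0.80/1.60 = 0.50 | 0.85 |

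Pooled alpha passes 0.6 in each row and within-person alpha fails in each. Person-mean alpha stays at 0.85 whatever rW is, so it carries almost no information about momentary consistency.

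**Step 2. When a pass can come from between-person differences alone.** Alpha reaches 0.6 when r = 0.6/(0.6 + 0.4k), which is 0.33 for 3 items and 0.23 for 5. With rW = 0, pooled r is p·rB, so the required between-person share is:
- 3 items: 0.333/0.8 = 42% (rB = 0.8) or 0.333/0.6 = 56% (rB = 0.6)
- 5 items: 0.231/0.8 = 29% or 0.231/0.6 = 38%

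**Step 3. When it cannot.** With 3 items and a correlation of 0.5 at both levels, pooled and within-person alpha are both 1.5/2.0 = 0.75, so nothing is masked. With 3 items, p = 0.5, rB = 0.6 and rW = 0, pooled alpha is 0.9/1.6 = 0.56, which correctly fails.

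**Step 4. Precision, only if an interval is added.** In simulations of 2,000 runs per setting, a standard (Feldt) 95% interval treating pooled beeps as independent was compared with the true spread of alpha. For 50 persons × 42 beeps, 3 items, p = 0.5, rB = 0.8 and rW = 0.1, the standard interval is 0.044 wide and the true 95% range is 0.157 (3.6 times), with coverage of 39%. Across all settings (3 or 5 items; 35, 42 or 70 beeps; p from 0.3 to 0.7) coverage runs from 24% to 56%, and the interval is about 2.5 to 6 times too narrow.

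**The case against.** The strongest reply is that the plan never says alpha is computed on pooled beeps. The compliance rule is set per day, and the missing-data sentence refers to analyses in general; missing beeps matter equally when beeps are averaged. Section 6.1 also uses alpha a second time, to check the rescaling of ESM scores, in a bullet about subject-level comparisons of seven-day means. This stands: beeps are the likelier reading of the internal-consistency bullet, but an inference. It does not remove the point, because person means leave momentary consistency untested as well.

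A reader might also infer that the plan's error bars are too narrow. The documents do not support this: alpha is a point value set against 0.6, and step 4 applies only to an interval that someone adds. Nor is alpha the only analysis without a multilevel method. The half-week correlation and the paired t-test against the single-time questionnaires are not multilevel either, though the t-test is justified at subject level.

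Finally, every magnitude above uses chosen inputs, and the item list is in an attachment that is not available. That stands too, and it is why step 3 is shown. The documents also cite 0.6 only as a general convention, not as a pass mark for person-centred items.

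**Conclusion.** The point holds as a gap in method. Section 6.1 leaves the unit of alpha open, and whichever of the two units is used, the coefficient cannot show that items cohere from moment to moment. This is more than a missing detail, because a better analysis exists for the same data.

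The size is conditional. Under the assumptions of step 1, a pass at 0.63 to 0.73 can accompany a within-person alpha of 0 to 0.50. With equal correlations at both levels the two agree. It would be tempting to conclude that the scale will pass falsely. The documents give neither the number of items, nor the variance shares, nor the correlations, so a false pass is possible but not demonstrated.

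**What to change.** In section 6.1:
- State the unit of analysis for every use of alpha, including the rescaling check.
- Report two coefficients for each scale: a within-person alpha or omega, from person-mean-centred items or a two-level model, and a between-person alpha from person means.
- Base any claim about momentary measurement on the within-person value, and apply the 0.6 convention at the level of intended use, chosen before the data are seen.
- If a confidence interval is reported, obtain it by resampling persons, not beeps.

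This costs some wording and a few extra lines of analysis, with no new data. The drawback is that the headline coefficient may be lower than a pooled alpha.

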3.4 Sample size calculation

The outcome of the ESM is multidimensional; it gives information about the (urological) complaints but also the context in which the complaints arise. An inter-individual analysis can be made with the use of ESM, and because of this extensive data can be collected per patient.

An appropriate sample size can therefore not be made.

In previous literature the sample size differs from N=5 ²⁷, N= 10 ³⁸, N = 19 ³⁹, N= 26 ¹ to N=40 ⁴⁰. In the study of Cabrita et. al. random slopes could not be included in the multilevel regression analysis because of the sample size being too small to validly estimate all associated parameters, but an individual analysis with linear regression models with random intercept has been made.³⁸ Other studies using ESM in a population between 19 to 40 patients have shown that clinically relevant differences could be detected using an alpha of 0.05.^{1,39-41} However, epidemiologic literature suggest that as a rule-of-thumb, a sample of at least N = 50 is required to evaluate construct validity^{42,43} and to recognize a factor pattern.⁴⁴ Therefore, we need to include at least 50 participants.

Empirical studies using ESM showed that about 5% to 23.2% of the patients did not comply (defined as completing the ESM questionnaire in less than 50% of the beeps).^{1,27,38-41} Taking into account a conservative non-valid ESM data rate of 23%, a sample size of 66 patients is needed to obtain 50 ESM questionnaires that can be used for the analysis.

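### Homogeneity of each ePRO item set is judged by Cronbach's alpha of at least 0.6 alone, which does not test for a single dimension; section 3.4 cites a factor pattern among its reasons for 50 patients, but section 6 plans no analysis of one.

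*Combined protocol and SAP*

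**What the plan says.** Section 6.1 (Primary study parameter) names one statistic for this property: "The homogeneity of a scale (*e.g.* internal consistency) is analysed by Cronbach's α-statistic". The limits follow directly: "A coefficient of at least 0.6 is generally considered as acceptable, values above 0.8 are considered as good to very good". The same section describes internal consistency as concerning items meant to capture similar symptoms or domains.

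Section 1, Part II, objective 3 states the hypothesis, "Therefore, we expect to find correlation coefficients (Cronbach's α) of >0.6", and bases it on the origin of the items: "since items were based on theoretical constructs as described in literature".

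Section 3.4 takes its minimum from a rule of thumb with two purposes. The first is that "a sample of at least N = 50 is required to evaluate construct validity"; the second is "and to recognize a factor pattern". It concludes: "Therefore, we need to include at least 50 participants". This is then raised to 66 for non-valid ESM data.

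Sections 6, 6.1 and 6.2 plan mixed models, delta scores and their predictors, alpha, half-week test-retest, paired t-tests and descriptive statistics. They contain no factor or component analysis, no other check of dimensionality, and no list of the items in each set. Alpha is used in one other place, to compare original with rescaled ESM data on the urological questions.

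**The concern.** Alpha summarises the average inter-item correlation and the number of items. It presupposes that the items share one dimension and cannot show that they do. A set made of two unrelated clusters can pass 0.6 if it is long enough, and section 6.1 would then call it acceptably homogeneous.

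This matters because the Summary makes the psychometric properties of the PROM the main outcome, and internal consistency is one of the five Part II objectives. With the grouping assumed from theory and no analysis able to contradict it, a passing alpha would confirm little about structure.

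Section 3.4 adds an inconsistency. A factor pattern is one of its two reasons for needing 50 patients, but no planned analysis looks for one.

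**Working it through.** **The plan's own figure.** Section 3.4 needs 50 evaluable patients and allows for 23% non-valid data; the upper end of the range it cites is 23.2%.
- 50 / (1 - 0.23) = 64.9, rounded up to 65.
- 50 / (1 - 0.232) = 65.1, rounded up to 66.

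The stated 66 is reproduced, exactly so with 23.2%. Nothing below changes it.

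**Inputs.** The limits 0.6 and 0.8 come from section 6.1 and n = 50 from section 3.4. The number of items k and the within-cluster correlation r are not in the documents. They are assumptions, shown as a range. The between-cluster correlation is set to 0, so the two halves have nothing in common.

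**Formula.** For k standardised items in two equal clusters:

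alpha = k/(k - 1) × [1 - 1/(1 + (k/2 - 1) r)]

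- k = 10, r = 0.3: 10/9 × (1 - 1/2.2) = 0.61.
- k = 10, r = 0.4: 10/9 × (1 - 1/2.6) = 0.68.
- k = 10, r = 0.5: 10/9 × (1 - 1/3.0) = 0.74.
- k = 6, r = 0.5: 6/5 × (1 - 1/2.0) = 0.60.
- k = 6, r = 0.6: 6/5 × (1 - 1/2.2) = 0.65.
- k = 4, r = 0.5: 4/3 × (1 - 1/1.5) = 0.44.

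Solved for the r at which alpha equals a limit t: r = [1/(1 - t(k - 1)/k) - 1] / (k/2 - 1).

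| Items | r for alpha 0.6 | r for alpha 0.8 |
|---|---|---|
| 4 | 0.82 | not reachable |
| 6 | 0.50 | only at r = 1 |
| 8 | 0.37 | 0.78 |
| 10 | 0.29 | 0.64 |
| 12 | 0.24 | 0.55 |
| 20 | 0.15 | 0.35 |

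**Would a dimensionality check help at n = 50?** A simulation used normal data, one score per person, two uncorrelated clusters and 5,000 runs per case. Parallel analysis used the 95th percentile.

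| Items, r | Alpha at least 0.6 | Two or more factors found |
|---|---|---|
| 6, 0.6 | 71% | 99% |
| 8, 0.5 | 84% | 99% |
| 10, 0.5 | 97% | over 99% |
| 12, 0.5 | 99% | over 99% |

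For sets that truly have one dimension (6 to 10 items, r = 0.3 or 0.5), the same check split them wrongly in under 0.5% of runs. In these clear-cut cases it separates what alpha at 0.6 does not. Unequal or correlated clusters would be harder to separate, and the simulation does not represent repeated beeps within a person.

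**The case against.** The strongest reply is that alpha is meant per domain. Section 6.1 speaks of items for similar symptoms or domains, and section 4.1.2 lists gastrointestinal, psychological, gynaecological and somatic symptoms separately. This stands. A reader might infer that the ePRO pools these domains into one mean score that is then treated as a single construct. The documents do not support that: section 6 uses day-means of individual symptoms, and the subject-means in 6.1 average over seven days. What remains is that membership of each set is assumed and not listed.

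Second, a reader might infer that the sample of 50 was chosen for a factor analysis. That goes too far. Construct validity is the first reason given, and section 3.4 does not announce a factor analysis. The gap is that one of two stated reasons has no matching analysis.

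Third, the sets may be short, since section 4.2.1 says items were cut to limit burden. This is fair: four items would need a within-cluster correlation of about 0.82. The questionnaire is an annex that is not part of the documents reviewed, so the set lengths are unknown here.

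Fourth, section 4.2.2 fills trigger questions with a negative default when no symptom is present. A factor analysis that included those items could recover the skip pattern instead of symptom dimensions. This is right, and the fix must leave them out.

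Focus groups and expert review do not answer the point. They support the relevance of items, not their dimensionality.

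**Conclusion.** The point holds in a limited form. As written, section 6.1 can label a two-dimensional item set homogeneous, and section 3.4 refers to a factor pattern that section 6 never examines. The risk is material for sets of about six or more items at moderate correlations and small for sets of about four. The 0.8 limit is much harder to pass by this route: ten items would need r of about 0.64.

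These sizes rest on assumed item counts, equal clusters and zero correlation between clusters. The consequence is confined to the conclusion on internal consistency and to any multi-item urological score, such as one that might be compared with the OAB-q, ICIQ-FLUTS or IPSS. The SR-BD comparison and the delta-score analyses of urgency use individual symptoms and are unaffected.

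**What to change.** In section 6.1:
- List the items of each intended set.
- Before alpha, run a factor analysis of the symptom items, for example with parallel analysis. Do this once on person-mean scores and once, separately, on person-centred beep scores. Leave out the trigger items that section 4.2.2 sets to a default.
- Report alpha for each set that is supported as one dimension, state the level at which it is computed, and report a set that splits as separate subscales.
- State that the person-level pattern from about 50 patients is imprecise.

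If this is not added, remove the factor-pattern reason from section 3.4 and do not describe alpha of at least 0.6 as evidence of homogeneity.

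The cost is one further analysis of data already collected. Factor analysis is available in the named software. Recruitment stays at 66 patients for 50 evaluable. The price is some added complexity in reporting if the person-level and beep-level patterns differ.
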